5.4 Inclusion Criteria

Women must meet all the following criteria to be eligible for inclusion in the study:

- 1) Age 18 through 45 years (inclusive) at screening
- 2) Able and willing to provide written informed consent.
- 3) Willing to use an effective method of birth control throughout the duration of the study. Examples of effective methods include: hormonal methods (other than NuvaRing®), IUD, bilateral tubal ligation, same sex partner, partner with a vasectomy, abstinence (defined as no vaginal sex for one month prior to screening).
- 4) Able and willing to provide adequate locator information
- 5) HIV-uninfected based on testing performed by study staff at screening (per algorithm in Appendix II)
- 6) In general good health as determined by the site clinician
- 7) Agree to be sexually abstinent, including use of sex toys, from V2 (Enrollment) until V7 (7 days after the biopsy visit) and 48 hours prior to all study visits.
- 8) Agree to refrain from use of vaginal device or products (for example, lubricants, creams, suppositories) throughout participation in the study. Tampons may be used except between V5 (biopsy visit) and V7 (day 14).
- 9) Willingness to undergo all study-related assessments and follow all study-related procedures
- 10) At screening and enrollment, agrees not to participate in other research studies involving drugs, medical devices, or vaginal products while enrolled in this trial
- 11) Participants over the age of 21 (inclusive) must have documentation of a satisfactory Pap within three years prior to Enrollment consistent with Grade 0 according to the Female Genital Grading Table for Use in Microbicide Studies Addendum 1 (Dated November 2007) to the DAIDS Table for Grading Adult and Pediatric Adverse Events, Corrected Version 2.1, July 2017, or satisfactory evaluation with no treatment required of grade 1 or higher Pap results. If no documentation of a Pap smear can be provided, a Pap smear will be collected at the screening visit.

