5.5 Exclusion Criteria

Women who meet any of the following criteria will be excluded from the study. Of note, the study is limited to premenopausal women with an intact uterus because the mucosal immune environment differs substantially between pre- and post- menopausal women. Therefore, inclusion of post-menopausal women would introduce heterogeneity into the population.

- 1.) Menopause (as defined as amenorrhea for one year or more without an alternative etiology)
- 2.) Hysterectomy
- 3.) Participant report of any of the following:
 - a) Known adverse reaction to any of the study products (ever)
 - b) Non- therapeutic injection drug use in the 12 months prior to Screening
 - c) Surgical procedure involving the pelvis in the 60 days prior to enrollment (includes dilation and curettage or evacuation, and cryosurgery; does not include cervical biopsy for evaluation of an abnormal pap smear)
 - d) Participation in a drug, spermicide and/or microbicide study in the 30 days prior to enrollment
 - e) Currently pregnant or pregnancy within 42 days prior to enrollment
 - f) Currently lactating
 - g) Use of a diaphragm, NuvaRing®, or spermicide for contraception
- 4.) Urogenital infection or suspected infection within 7 days of enrollment including: symptomatic candidiasis, trichomonas vaginalis, and symptomatic bacterial vaginosis; or cervical infection, including *N. gonorrhoeae* (GC), *C. trachomatis* (CT), or mucopurulent cervicitis; syphilis; HSV lesions, or other sores (Note: seropositive HSV without active lesions will not be excluded); acute pelvic inflammatory disease; urinary tract infection; recent exposure to a partner with GC, CT, Trichomonas, syphilis, or NGU
- 5.) Antibiotic or antifungal therapy (vaginal or systemic) within 7 days of enrollment
- 6.) As determined by the PI, has any significant uncontrolled active or chronic cardiovascular, renal, liver, hematologic, neurologic, gastrointestinal, psychiatric, endocrine *including poorly controlled diabetes), respiratory, immunologic disorder or infectious disease
- 7.) Menses-like bleeding at the time of the Enrollment visit* or expected menses-like bleeding within 14 days of the Enrollment visit
(*Women who have vaginal bleeding at the scheduled Enrollment visit may return at a different date to be re-examined and possibly enrolled provided they are still within the screening window and meet all criteria.)

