7.2 Visit 1: Screening Visit

Screening may take place up to 45 days prior to Enrollment. Screening procedures may occur over several visits. A combined written informed consent for screening and enrollment will be obtained before any screening procedures are initiated. For participants who do not meet the eligibility criteria, screening will be discontinued once ineligibility is determined.

The table below outlines procedure to take place at the Screening visit.

Table 1: Visit 1 Procedures

VISIT 1: SCREENING VISIT	
Component	Procedure/Analysis
ADMINISTRATIVE	
 • Written Informed Consent • Assign Study Number (PTID) • Review Eligibility • Collect Contact Information • Medical history and concomitant medications • Visit Questionnaire • HIV Pre-/Post-Test Counseling • Screening Results • Protocol counseling (including effective birth control, sexual practices restrictions and vaginal product use) • Schedule Next Study Visit, prn • Participant Reimbursement
URINE	
 • Pregnancy test • Urine dipstick, as clinically indicated
SALIVA	
 • Rapid HIV
BLOOD	
 • Confirmatory HIV, as clinically indicated
VAGINAL	
 • pH • Wet Mount, as clinically indicated • Trichomonas (NAAT) • Vaginal sample for Future Use*
CERVICAL	
 • GC/CT (NAAT) • Cervical sample for Future Use* • Pap smear, as indicated
CVL	
 • Levels of antiviral activity • Levels of glycoproteins and mucins • Levels of cytokines & innate immunity factors • Assessment of drug assay specificity for MK-2048 and Eudragit®
PHYSICAL EXAM	
 • Physical Exam • Vital Signs (BP) • Height & Weight
PELVIC EXAM	
 • Bimanual Exam, as clinically indicated • External Genital & Speculum Exam

* For participants who have consented to the collection of samples for future use and use of left-over samples for future studies.

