7.4 Visit 3, 4, 5, 6, 7 and 8: Follow-Up Visits

Visit 3, 4, 5, 6, 7 and 8 procedures are outlined in Table 4. The windows around these study visits are as follows:

Visit 3: Day 3 (2-4)

Visit 4: Day 5 (5-6)

Visit 5: Day 7 (7-8)

Visit 6: Day 10 (9-12)

Visit 7: Day 14 (13-16)

Visit 8: Day 28 (24-32)

Two cervical biopsies will be obtained at Visit 5 only. A CVL will be performed at Visits 7 and 8. Residual drug, if present, will be removed during the CVL at Visit 7. The purpose of Visit 8 is to provide a final safety assessment.

Table 3: Follow-up Visit Procedures

VISIT 3, 4, 5, 6, 7, 8 FOLLOW-UP VISITS	
Component	Procedure/Analysis
ADMINISTRATIVE	
 • Collect/Update Contact Information • Visit Questionnaire • Update medical history and concomitant medications • Protocol counseling excluding Visit 8 (including effective birth control, sexual practices restrictions and vaginal product use) • Assess/Document Adverse Events • Schedule Next Study Visit (excluding Visit 8) • Participant Reimbursement
ACCEPTABILITY	
 • Acceptability Questionnaire (Visit 5 ONLY; prior to biopsy)
BLOOD	
 • MK-2048 level
URINE	
 • Pregnancy test (Visit 5 & 8 and as clinically indicated) • Urine dipstick, as clinically indicated
VAGINAL	
 • pH • Wet Mount, prn • Trichomonas (NAAT), as clinically indicated • Gram Stain • Quantitative Vaginal Culture • Quantitative PCR for microbiota • Vaginal swab for MK-2048 level • Vaginal sample for Future Use*
RECTAL	
 • Rectal swab for MK 2048 (Visit 5 ONLY)
CERVICAL	
 • GC/CT (NAAT), as clinically indicated • Cervical biopsies- two adequate (Visit 5 ONLY) • Cervical sample for Future Use*
CVL (Visits 7 and 8 only)	
 • Levels of antiviral activity • • Levels of glycoproteins and mucins • Levels of cytokines & innate immunity factors • MK-2048 level • Eudragit® levels
PHYSICAL EXAM	
 • Physical Exam, as clinically indicated • Vital Signs (BP)

PELVIC EXAM	
 • Bimanual Exam, as clinically indicated • External Genital & Speculum Exam
--------------------	--

* For participants who have consented to the collection of samples for future use and use of left-over samples for future studies.

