9.3.2 Secondary and Exploratory Endpoints

The secondary and exploratory endpoints of this study are as follows:

Secondary: MK-2048 pharmacokinetics

MK-2048 concentrations in plasma, tissue homogenate, and CVL rectal and vaginal swab eluents, comparing the two film formulations sampled at enrollment and post-enrollment time-points through Visit 8

Secondary: Acceptability

Reports of overall acceptability of the film and qualities of the experience with the film will be measured using a self-report survey drawing items from two sources. Overall acceptability is measured using standard language in market research methodology, each using a 5-point agreement scale followed by an open-ended explanation. Assessment of film-specific qualities of the experience is assessed by a 9-item scale drawn from previous research with participant-inserted films. Questions assess perceptions of leaking, vaginal dryness, and sensation of the film inside the vagina during and after insertion.

Exploratory: Vaginal Microenvironment

Given that there is no non-product use arm, participants will serve as their own control. Assessment of baseline microenvironment will take place during the Enrollment visit with the

exception of CVL properties. CVL will be obtained at the Screening visit so that the microenvironment can recover prior to study product administration at the enrollment visit.

Levels of lectin binding and mucins measured in CVL samples

Endogenous and exogenous glycolytic enzymes, formulated microbicide products, and microbial flora interact with mucins and may alter their structure and function. These alterations may be detected with lectins, which are sugar specific binding molecules, and can be bound to reporter molecules (such as horseradish peroxidase) in an ELISA type assay.

Nugent Score

Clinically significant changes in vaginal flora will be evaluated by a change in the Nugent score baseline (Visit 2, pre-exposure) through Visit 7. The Nugent score is graded 1 to 10 as follows:

Normal, 0 to 3

Intermediate, 4 to 6

BV, 7-10

Any shift from normal at baseline to intermediate or BV at Visit 3, 4, 5, 6, 7, or 8 or shift from intermediate or BV to normal at Visit 3, 4, 5, 6, 7, or 8 will be considered a scientifically meaningful change in vaginal microbiota.

Quantitative vaginal cultures and quantitative PCR

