Meaningful changes will be defined by greater than or equal to 1 log changes in dominant members of the microbiota, including *Lactobacillus* species, *Gardnerella vaginalis*, key anaerobic microorganisms, *Enterococcus* species, *Escherichia coli*, *Staphylococcus aureus*, Group B *Streptococcus*, and *Candida* species.

Levels of anti-viral activity in CVL

In-vitro anti-HIV activity will be determined by the TZM-bl assay.

The TZM-bl assay will determine HIV-1 infection by luciferase for single round of replication. To assess the potency of the CVL, serial dilutions will be made and tested to determine the IC₅₀.

Levels of biomarkers of innate immunity

Changes in cervical cytokine expression and innate immunity factors in cervicovaginal lavage will be assessed. Changes within each group will be reported. The factors to be analyzed will be determined on the scientific evidence at the time of the analysis.

Exploratory: Pharmacokinetic (PK)/ Persistence of Eudragit® in CVL

Persistence of polymer will be determined as detected levels of polymer in vaginal fluid collected through cervicovaginal lavage.

Exploratory: Ex vivo challenge

HIV infection of cervical biopsies as measured by HIV-1 p24 replication by ELISA and confirmation either by immunohistochemistry or quantitative PCR assessment of integrated provirus in HIV-1- exposed cervical biopsies.

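### Between-arm tests of CVL markers and microbial quantity are not adjusted for the collected baseline, and within-arm CVL change cannot be attributed to the film alone (minor)

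*Combined protocol and SAP*

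**What the plan says.** - **Design.** Section 9.3.2 states "Given that there is no non-product use arm, participants will serve as their own control". Of the innate-immunity markers in lavage it adds "Changes within each group will be reported".
- **Sampling.** Section 7.4 states "Two cervical biopsies will be obtained at Visit 5 only. A CVL will be performed at Visits 7 and 8". The only earlier lavage is at screening, and section 7.2 says "Screening may take place up to 45 days prior to Enrollment". Section 7.4 also says "Residual drug, if present, will be removed during the CVL at Visit 7". Swabs for Gram stain, culture and qPCR are taken at Visit 2 before the film, and at every visit from Visit 3 to Visit 8.
- **Analysis, 9.7.3.** CVL markers are compared between arms by t or Mann-Whitney tests, on levels and also on pre-to-post change. Within each arm, change is tested by paired t or signed-rank tests. Mixed models relate outcomes to days of exposure. Microbial quantity and its change are compared by Mann-Whitney tests. No model with a baseline covariate is named, and the plan does not say whether levels or changes lead.
- **Adverse events.** Section 9.2 justifies N = 48 by exact binomial intervals for the Grade 2+ proportion. Section 9.7.2 and Table 5 name frequencies and percentages, and 9.7.2 adds tabulation by relationship and Fisher's exact test. Neither names an interval.

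**The concern.** Three gaps would affect how results are read.

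1. The stated exploratory objective is to compare the two formulations. The randomized comparison answers it, and the plan leaves precision unused there by not adjusting for a baseline it already pays to collect.
2. The own-control comparison for CVL has no post-dose sample before the biopsies. A cytokine or mucin change at Day 14 could be reported as a film effect when tissue healing, or the distance from the screening sample, would explain it equally well.
3. The interval that sized the trial is not carried into the primary analysis. The all-cause primary runs through Visit 8 and can include biopsy events, so readers would want the product-related proportion beside it, with its own interval.

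**Working it through.** **Step 1. The plan's own figures.** Two-sided 95% Clopper-Pearson limits reproduce section 9.2: 0/48 has an upper limit of 7.4%; 5/48 gives 3.47% to 22.66% (Table 4: 3.4% to 22.6%); 3/24 gives 2.66% to 32.36% (Table 4: 2.7% to 32.4%). Every row of Table 4 agrees within 0.1 percentage point.

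**Step 2. Baseline adjustment.** Input from 9.2: n = 24 per arm. The correlation r between baseline and follow-up is not in the documents, so I assume 0.3, 0.5 and 0.7. In units of the outcome SD:
- post-dose level only: SE = √(2/24) = 0.289
- raw change: SE = 0.289 × √(2(1 − r))
- ANCOVA: SE = 0.289 × √(1 − r²)

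| r | Level | Change | ANCOVA | n per arm for level to match, 24/(1 − r²) | n per arm for change to match, 48/(1 + r) |
|---|---|---|---|---|---|
| 0.3 | 0.289 | 0.342 | 0.275 | 26.4 | 36.9 |
| 0.5 | 0.289 | 0.289 | 0.250 | 32.0 | 32.0 |
| 0.7 | 0.289 | 0.224 | 0.206 | 47.1 | 28.2 |

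The fair comparator in each row is the better planned test: about 26, 32 and 28 per arm against 24. These are large-sample formulas; simulated ANCOVA standard errors at this n were 0.277, 0.251 and 0.207.

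**Step 3. Lavage timing.** From the visit windows in 7.4 (Visit 5 Days 7–8, Visit 7 Days 13–16, Visit 8 Days 24–32):
- biopsy to Visit 7 lavage: 13 − 8 = 5 to 16 − 7 = 9 days
- biopsy to Visit 8 lavage: 24 − 8 = 16 to 32 − 7 = 25 days
- longest gap from screening lavage to Visit 7: 45 + 16 = 61 days; to Visit 8: 45 + 32 = 77 days

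No lavage falls between film insertion and biopsy. Visits 3 (Days 2–4) and 4 (Days 5–6) do, but they yield swabs only.

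**Step 4. The days-of-exposure model for CVL.** Counted from insertion, exposure is 0, 14, 28 days and post-biopsy status is 0, 1, 1. Their correlation is 0.87, so VIF = 1/(1 − 0.75) = 4.0. If exposure stops at the Visit 7 removal (0, 14, 14), the correlation is 1.00. In the first coding only the assumed straight line separates the two; in the second nothing does. The plan does not say which applies.

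**Step 5. What a non-film shift would do.** The size of any biopsy effect cannot be derived from the documents. The percentages below are conditional on an assumed shift of 0.25, 0.5 or 0.75 SD with no film effect.
- Paired t-test, n = 24, r = 0.5: significant in about 22%, 65% and 94% of trials. For 0.5 SD, r from 0.3 to 0.7 gives about 51% to 86%.
- Days slope, 48 women, 0/14/28 days, r = 0.5: about 5%, 4% and 2% if the shift is present at Visit 7 only; about 13%, 37% and 66% if halved by Visit 8; about 40%, 92% and over 99% if undiminished at Visit 8. Repeat simulations differ by one or two points.
- Between-arm test of change, same shift in both arms: about 5% throughout.

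**Step 6. All-cause against product-related events.** In the earlier placebo-film study (section 2.4), 6 Grade 2 events occurred among 64 women and 2 were attributed to product. Assuming each was in a different woman, that is 6/64 = 9.4% (3.5% to 19.3%) against 2/64 = 3.1% (0.4% to 10.8%). This shows how far the two measures can differ; it is not an estimate of a biopsy effect.

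**The case against.** Much of the case on the other side stands.

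- **A reader might infer that the between-arm tests ignore baseline.** They do not. Section 9.7.3 plans between-arm tests of change for CVL markers and for microbial quantity. Under randomization both these and the level tests are valid. The ANCOVA point is about precision and about naming one lead analysis.
- **A reader might infer that biopsy undermines the formulation comparison.** All women are biopsied at the same visit, so an effect equal in both arms cancels.
- **A reader might extend the problem to every microenvironment endpoint.** Nugent, culture and qPCR samples at Visits 3 and 4 come after dosing and before biopsy, so own-control comparisons there are free of it.
- **A reader might blame the end of the abstinence and tampon rules for a Visit 8 change.** Section 5.4 applies continuous abstinence from Visit 2 to Visit 7 and bars tampons only from Visit 5 to Visit 7, with 48-hour abstinence before all visits. Screening and Visit 8 both lie outside the continuous restrictions, so it is Visit 7 that differs from baseline in this respect.
- **A reader might take the high days-model percentages as expected error rates.** They need a shift undiminished 16 to 25 days after biopsy; if it has gone by Visit 8 the slope is not inflated at all.
- **The all-cause primary is a legitimate choice.** Relatedness is already tabulated, and section 10.2.1 says biopsy cramping typically passes within minutes. The related-event interval is a reporting addition. The absence of an interval for the all-cause primary is the clearer omission, given how N was justified.

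**Conclusion.** The point holds in a limited form and is minor.

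- No between-arm comparison of CVL markers or microbial quantity in 9.7.3 is baseline-adjusted. Against the better planned test, the gain from ANCOVA is equivalent to roughly 2 to 8 extra women per arm over assumed correlations of 0.3 to 0.7.
- For CVL endpoints only, within-arm change and the exposure slope mix film, biopsy and the timing of the screening baseline. This follows from the visit schedule and needs no assumption. How large the distortion would be is unknown, and every false-attribution percentage above depends on an assumed shift.
- Section 9.7.2 and Table 5 do not carry forward the exact interval on which 9.2 rests.

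The CVL marker and microbiota endpoints are exploratory, and the randomized contrast that addresses their stated objective is sound, provided any biopsy effect is the same in both arms.

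**What to change.** 1. **Section 9.7.3, between arms.** For continuous CVL and microbial-quantity endpoints, make ANCOVA on the collected baseline (Visit 1 lavage; Visit 2 culture or qPCR) the lead analysis, on the log scale or ranks where skewed, with the unadjusted result alongside.
2. **Section 9.7.3, within arms.** Base CVL inference about formulation on the between-arm contrast. Report within-arm CVL change and the CVL exposure slope as descriptive and not attributable to the film alone. Give the reasons: biopsy and the timing of the screening baseline at both visits; at Visit 7, abstinence and tampon restrictions not in force at screening; at Visit 8, the preceding lavage and removal of residual drug. State whether exposure days stop at that removal.
3. **Section 9.7.2 and Table 5.** Report the exact 95% interval for the all-cause Grade 2+ proportion, by arm and overall, with the product-related Grade 2+ proportion and its exact interval beside it. A table of onset before or after biopsy is optional.

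The cost is SAP wording and a few tables. Visits, procedures and N are unchanged. Intervals for small related counts will be wide: 0/24 still has an upper limit of 14.2%.

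### The baseline lavage is taken at Screening, where the bleeding, infection and anti-infective exclusions do not apply, so within-arm changes in the exploratory CVL endpoints can be confounded

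*Combined protocol and SAP*

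**What the plan says.** **Where the baseline is taken.** Section 9.3.2 (Vaginal Microenvironment) notes that there is no untreated arm and uses each woman as her own control. Most baselines are set at Enrollment, but the lavage is the exception: "CVL will be obtained at the Screening visit so that the microenvironment can recover prior to study product administration at the enrollment visit". Table 1 and Appendix 1 agree.

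**How early it may be.** Section 7.2: "Screening may take place up to 45 days prior to Enrollment". It sets no minimum. It also says "Screening procedures may occur over several visits".

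**Where the conditions are anchored.** Section 5.5 excludes "Menses-like bleeding at the time of the Enrollment visit", or bleeding expected in the 14 days that follow. It also excludes "Antibiotic or antifungal therapy (vaginal or systemic) within 7 days of enrollment" and urogenital infection in the same 7-day window. Section 7.3 checks for bleeding, and reschedules for it, at Enrollment only. Nothing postpones or repeats a Screening lavage for bleeding, infection or treatment.

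**Abstinence.** Section 5.4, item 7, asks women to agree to abstain for "48 hours prior to all study visits". Section 7.2 places consent at the start of Visit 1: "A combined written informed consent for screening and enrollment will be obtained before any screening procedures are initiated".

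**How the lavage is used.** Section 9.7.3 tests pre- to post-exposure change within each arm (paired t or signed-rank) and compares change between arms (t or Mann-Whitney). The post-dose lavages are at Visit 7 (days 13-16) and Visit 8 (days 24-32).

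**The concern.** The conditions that keep the genital tract comparable are applied on a different day from the baseline they should protect. A woman may be bleeding, infected or on an anti-infective when the lavage is taken, recover or be treated (Section 8.5 provides for treating infections found during screening), meet every Enrollment rule, and be randomized with that baseline.

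The first post-dose lavage is better protected. Bleeding expected within 14 days of Enrollment is excluded, and abstinence runs from Visit 2 to Visit 7. Baseline and Visit 7 samples can therefore differ for reasons unrelated to the film, and no untreated arm shows how much. If blood or infection raises inflammatory markers at baseline, a real rise after the film would be partly hidden. That is the unwelcome direction for films that Section 10.2.1 describes as not previously tested in humans.

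A disturbed baseline would also be hard to recognize later. Gram stain, culture and qPCR start at Enrollment, and wet mount at Screening is done only if indicated.

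Finally, early lavage is meant to allow recovery before dosing, but only a maximum interval is stated. A lavage shortly before Visit 2 would be permitted, and the baseline Gram stain, culture and qPCR are taken at that visit.

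**Working it through.** The plan gives no figure on this point, so there is none to reproduce.

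**1. Date arithmetic** (Sections 5.5, 7.2, 7.4 and 4.6; Synopsis)
- Reach of the 7-day exclusions: the look-back misses the lavage when the gap exceeds 7 days. Of gaps of 1 to 45 days, that is days 8 to 45: 45 - 7 = 38, and 38/45 = 84%. This is a share of permitted gap lengths, not of women.
- Expected gap: participation of 5-10 weeks less 4 weeks after Enrollment gives 35 - 28 = 7 to 70 - 28 = 42 days. Most expected gaps lie beyond the look-back.
- Longest pre/post interval: 45 + 16 = 61 days to Visit 7, and 45 + 32 = 77 days to Visit 8.

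**2. How many baselines could be affected.** The documents do not say. For bleeding alone, assume a 28-day cycle, 5 bleeding days and a random screening day: 5/28 = 17.9%. Applied to all 24 women in an arm, this is 4.3. It treats every woman as cycling, although Section 5.4 admits users of hormonal methods, and it falls toward 0 if staff avoid menses. The range is about 0 to 4 per arm.

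**3. Effect on the two kinds of comparison.** Assume n = 24 per arm, SD 1 before and after, pre/post correlation 0.5 and no film effect. A fraction f of baselines is raised by d SD, with the same f in both arms because the lavage precedes randomization.
- Shift in mean within-arm change = -f × d. Smallest: 0.1 × 0.5 = 0.05 SD. Largest: 0.3 × 1.5 = 0.45 SD.
- SD of change = √(1 + f(1 - f)d²). Smallest: √(1 + 0.0225) = 1.01. Largest: √(1 + 0.4725) = 1.21.
- Expected between-arm difference in change = -fd - (-fd) = 0.

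Simulation (10,000 trials per setting, two-sided 5% t-tests):

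| f | d | Within-arm shift (SD) | Within-arm type I error | Between-arm type I error | SD of change |
|---|---|---|---|---|---|
| 0 | – | 0.00 | 5.0% | 5.4% | 1.00 |
| 0.1 | 0.5 | -0.05 | 5.9% | 4.9% | 1.01 |
| 0.2 | 1.0 | -0.20 | 14.2% | 4.9% | 1.08 |
| 0.3 | 1.5 | -0.45 | 41.0% | 5.4% | 1.21 |

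The within-arm test reports change that the film did not cause. The between-arm test keeps its level but loses precision: in the worst row, 24/1.4725 = 16.3, so 24 women per arm carry the information of about 16.

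**The case against.** **The conditions are not all tied to Enrollment.** On its wording the 48-hour abstinence covers Visit 1, and the vaginal-product restriction runs throughout participation. A reader might infer that no safeguard reaches the Screening lavage; the text does not support that. Women could also be told of the abstinence rule at pre-screening (Section 7.1). What stands is that the agreement is formally made at Visit 1, so it cannot be relied on when consent and lavage fall on the same day. Bleeding, infection and anti-infectives have no counterpart at Screening.

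**The formulation comparison is sound.** A reader might infer that every pre/post CVL comparison is biased. It is not: disturbed baselines are expected equally in both randomized arms, and the exploratory objective is to compare the formulations. This stands in full and confines the bias to within-arm change, which Sections 9.3.2 and 9.7.3 nevertheless plan to report and test.

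**Post-dose samples may be disturbed too.** Visit 8 lies outside the 14-day bleeding rule, so cleaning the baseline alone could create a new imbalance. This stands, and the fix must cover every lavage.

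**Much is already recorded.** Screening includes history, medications, speculum exam, pH, and trichomonas, gonorrhea and chlamydia tests, and site SOPs may add more. This helps a sensitivity analysis, but the plan specifies none.

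**The expected gap is at least a week.** The expected participation implies about 7 days or more, so a lavage a day or two before Visit 2 is unlikely. That is an expectation, not a rule.

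**The endpoints are exploratory, and Table 5 lists only descriptive statistics for them.** True, but a described change carries the same shift as a tested one.

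**Conclusion.** The concern holds for within-arm changes in the exploratory CVL endpoints: cytokines and innate factors, glycoproteins and mucins, and antiviral activity. Their baseline may be taken during bleeding, infection or treatment, and nothing in the plan prevents or adjusts for it.

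The date arithmetic follows from the documents. The size of the bias does not. The 0.05 to 0.45 SD shift and the 6% to 41% type I error rest on the assumed fractions and shifts, and the direction for a given marker is unknown.

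It should not be read more widely. Between-arm comparisons of change stay unbiased with some loss of precision. The primary adverse-event endpoint and the plasma, swab and tissue PK do not use this sample. The Nugent, culture and qPCR baselines are taken at Enrollment under the Enrollment rules; for them only the missing minimum interval matters. The Screening MK-2048 and Eudragit assays are specificity checks.

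This is a cheap improvement to exploratory work, not a threat to the trial's main conclusion.

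**What to change.** 1. **Section 7.2 and Table 1:** collect the baseline CVL only if the existing bleeding, infection, anti-infective and 48-hour abstinence conditions are met on that day. Otherwise defer it to another screening visit, which 7.2 already allows.
2. **Section 7.2:** state a minimum interval from lavage to Enrollment, so that the recovery purpose in 9.3.2 is secured. The documents give no recovery time, so the protocol team must set and justify the length. The 7 days in exclusions 4 and 5 are at most an example.
3. **Section 7.4, Tables 1 and 3:** record bleeding, infection, treatment and cycle day at every CVL (Screening, Visits 7 and 8).
4. **Section 9.7.3:** add a sensitivity analysis of within-arm change that excludes pairs with a disturbed baseline or post-dose sample. Keep all pairs in the main analysis.

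**Cost:** a short amendment and a few data fields, with no added participants. Some women need a second screening visit, probably with another speculum exam, and the payment table in 10.3 shows a single Visit 1 payment. The sensitivity analysis will have fewer than 24 pairs per arm.
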